7.3.3.3. Electrocardiograms (ECG)

Descriptive statistics by visit and treatment group will be presented for each ECG parameter (including PR, QRS, QT, and QTcF) values and for change from baseline values.

- QT, QTcF interval > 450 msec
- QT, QTcF interval > 480 msec
- QT, QTcF interval > 500 msec
- QT, QTcF interval increases from baseline > 30 msec
- QT, QTcF interval increases from baseline > 60 msec

A by-patient listing of ECG results will be presented.

7.3.3.4. Immunogenicity

All immunogenicity analyses will be conducted on the Safety Set. The number and percentage of patients developing ADA and anti-drug neutralizing antibodies, where applicable, will be summarized by naïve, previously eculizumab-treated patients, and total.

7.3.3.5. Non-Drug Therapies and Procedures

By-patient listings of non-drug therapies and procedures will be produced.

9. APPENDICES

9.1. Protocol Schedule of events

Refer to the protocol for a schedule of events.

9.2. Changes from Analyses Specified in the Previous Version of the SAP

This study is descriptive in nature and not statistically powered for hypothesis testing due to the rarity of disease in pediatric patients. Approximately 13 patients will be enrolled to ensure at least 10 evaluable patients complete the 26-week period, which is expected to be sufficient to adequately describe PK/PD in pediatric patients with PNH.

9.3. Sample Size, Power, and Randomization

The following derived data will be calculated prior to analysis.

Age

Age will be presented as the number of years between date of birth and the reference date. The following ages (in years) may be computed using the formula (reference date – date of birth) + 1/365.25, with reference dates indicated as follows:

Table 3: Age and Reference Date

AGE	REFERENCE DATE
• Age at Enrollment	• Date of Signing ICF
• Age at PNH Diagnosis	• Date of PNH diagnosis
• Age at First Infusion	• Date of First Infusion

For all dates, in cases where only the month and year are provided for a date, the day for the date will be imputed as 15. Missing month will be imputed as June. In cases where the day is observed but the month is missing, the date will be imputed as June 15.

Disease Duration

Paroxysmal nocturnal hemoglobinuria disease duration will be presented as the number of years between the date of first study drug infusion and the date of PNH diagnosis (ie $INT [(Date\ of\ first\ infusion - Date\ of\ PNH\ diagnosis + 1)/365.25]$ or a similar formula using months and years or years only in the event of partial dates for PNH diagnosis)

Definition of Baseline Values

Baseline for LDH is defined as the average of all available on study assessments prior to the first study drug infusion. Baseline for all other parameters is defined as the last non-missing assessment value prior to first study drug infusion unless otherwise specified.

Change From Baseline

Change in values from baseline will be calculated as follows:

Change in Value = (subsequent value – baseline value), given that both the baseline value and subsequent value are non-missing.

Percent Change in Assessments From Baseline

Percent change in values from baseline will be calculated as follows:

% Change in Value = Change in Value/ Baseline value × 100; where change in value = (subsequent value – baseline value), given that the baseline value is non-missing and non-zero and the subsequent value is non-missing.

Analysis Visits

Study visits will be defined through the use of windows based on the list of visits described in the schedule of assessments of the protocol. For all assessments, the number of days from baseline will be calculated using the following formula: (date of assessment) - (date of first study treatment) + 1. This number of days will be used to assign analysis visits. This may not always correspond to the electronic case report form (eCRF) visit.

All post baseline records including those that occurred outside the specified protocol windows will be assigned to an appropriate analysis visit by using the following scheme and will be included in the analysis of the specific assessment, where applicable.

Generally, the lower bound and the upper bound for each analysis visit window is defined as the midpoint of the target dates between 2 consecutive scheduled visits. The upper bound of the last visit window is set as the target date + 7 days. If the date of assessment falls in between the lower bound and the upper bound for a visit as defined in the protocol schedule of assessment, then it will be assigned to that visit. If the interval separating 2 scheduled visits is an even number of days, that middle day will be included in the lower bound of the next visit window.

For example, for an assessment with a scheduled visit on Day 127, and a prior scheduled visit on Day 99 and subsequent scheduled visit on Day 155, the window will start at 113 days from baseline and will go to 140 days from baseline.

If only 1 record is within an analysis visit window, the data from that record will be used in the analysis. If more than 1 record is within the same analysis visit window, the record closest to the midpoint of the interval will be used in the analysis. If 2 records are “tied” before and after the middle of the interval, the earlier record will be used in the analysis.

Please refer to the following table for visit window definitions.

Table 4: Visit Window

Endpoint	Visit	Nominal Day	Start (Day)	End (Day)
Chemistry/Hematology/ Vital Signs	Screening		-28	0
	Day 1	1	1	1
	Day 15	15	8	28
	Day 43	43	29	56
	Day 71	71	57	84
	Day 99	99	85	112
	Day 127	127	113	140
	Day 155	155	141	168
	Day 183	183	169	196
FACIT Fatigue/Urinalysis	Screening		-28	0
	Day 1	1	1	1
	Day 15	15	8	42
	Day 71	71	43	98
	Day 127	127	99	154
	Day 183	183	155	210
	PNH Clone	Screening		-28
	Day 1	1	1	1
	Day 71	71	36	126
	Day 183	183	127	266

Adverse Events

Treatment-emergent AEs (TEAEs) are events with start dates and start times on or after the date and time of the first ALXN1210 dose. If the start date of an AE is partially or completely missing and the end (stop) date and time of the AE does not indicate that it occurred prior to first dose, then the determination of treatment-emergent status will be based on the following:

- If the start year is after the year of the first study drug dose, then the AE is treatment-emergent; else,
- If the start year is the same as the year of the first study drug dose and
 - the start month is missing, then the AE is treatment emergent; else if
 - the start month is present and is the same or after the month of the first study drug dose, then the AE is treatment-emergent; else.
- If the start date is completely missing, then the AE is treatment-emergent.

All other AEs are considered Pre-Treatment Adverse Events (PTAEs).

Patient percentages are based on the total number of treated patients in the particular group including naïve, previously eculizumab-treated patients and total.

Related AEs are defined as possible, probable, or definitely related. Unrelated AEs are defined as unlikely or not related.

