An interim analysis of data, including ALXN1210 PK and free C5 levels, will be conducted after 4 patients weighing ≥ 5 kg to < 40 kg have completed dosing through Day 71. Enrollment of patients will proceed without interruption while the analysis is ongoing. The accrued safety and PK/PD data will be assessed to ensure that ALXN1210 treatment is well tolerated and is providing adequate complement inhibition. Based on this review, the dose regimen may be adjusted. In addition, an independent Data Monitoring Committee (DMC) will review safety data from the study on a regular basis. Prior to the initiation of the study, the committee will develop a charter to describe their activities and responsibilities.

To support regulatory filings, interim analyses may be conducted based on efficacy, safety, PK, PD, and immunogenicity data collected through the end of the 26-week Primary Evaluation Period (Day 183) after 12 patients are enrolled, and after enrollment is completed.

After completion of all pre-dose assessments on Day 183, all patients will enter an Extension Period and continue to receive ALXN1210 according to the appropriate weight-based regimen. The Extension Period will continue until the product is registered or approved (in accordance with country-specific regulations) or for up to 4 years, whichever occurs first, except in Norway where the Extension Period will be 4 years. The end of study is defined as the last patient's last visit or follow-up (whether on site or via phone call) in the Extension Period.

The study objectives are as follows:

The objectives of this study are to assess the pharmacokinetics (PK), pharmacodynamics (PD), safety, and efficacy of ALXN1210 in pediatric patients with paroxysmal nocturnal hemoglobinuria (PNH). Additional information about the study can be found in the protocol.

To support regulatory filings, interim CSRs may be prepared based on efficacy, safety, PK, PD, and immunogenicity data collected through the end of the 26-week Primary Evaluation Period (Day 183) after 12 patients are enrolled, and after enrollment is completed. This statistical analysis plan (SAP) outlines only the analyses that are to be included in the report developed after the 26-week Primary Evaluation Period after 12 patients are enrolled. A final CSR to summarize long-term efficacy, safety, PK, PD, and immunogenicity parameters will be produced at study completion.

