7.2.2. Secondary Analyses

Descriptive statistics for the secondary endpoints will be produced for each visit where applicable, by naïve, previously eculizumab-treated patients and total.

- Percentage change in LDH from baseline to Day 183 (Week 26)
 - Absolute LDH levels, and the change and percent change from baseline, will be summarized at all study visits up to Day 183 (Week 26) by both observed case (OC) and LOCF. Baseline is defined as the average of all assessments analyzed by the central laboratory prior to first study drug administration.
 - The number (%) of patients achieving LDH levels at or below 1.0 times upper limit of normal ($1.0 \times \text{ULN}$) and levels at or below $1.5 \times \text{ULN}$ will be displayed.
 - Mean ($\pm 95\%$ CI) of absolute LDH levels, and the change and percent change from baseline will be plotted over time, by naïve and previously eculizumab-treated patients.
- Transfusion avoidance (TA)
 - Point estimates and 2-sided 95% exact CIs will be computed. Patients who withdraw from the study due to lack of efficacy during the Primary Evaluation Period will be considered as non-responders and will be counted in the group

- needing transfusion. For patients who withdraw from the study for any other reason during the Primary Evaluation Period, their data up to the time of withdrawal will be used to assess TA.
- A summary of the number of pRBC transfusion requirements up to Day 183 study will be presented including number of transfusion episodes and units transfused.
 - Change in quality of life (QoL), as measured by Pediatric FACIT-Fatigue questionnaire from baseline to Day 183 (Week 26)
 - The scoring guideline for the Pediatric FACIT-Fatigue instrument will be used to calculate a FACIT-Fatigue score. Please refer to Section 9.4 for a more detailed description of the Pediatric FACIT-Fatigue score and the scoring methods.
 - Absolute scores, change from baseline, and percent change from baseline in FACIT-Fatigue scores will be summarized by both OC and LOCF at baseline and at the study visits where this assessment is collected up to Day 183 (Week 26).
 - At each study visit, the proportion of patients who showed an improvement of at least 3 points for the Pediatric FACIT-Fatigue scores will be summarized by point estimates and 2-sided 95% exact CIs.
 - Proportion of patients with stabilized hemoglobin

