7.3. Safety Analyses

All safety analysis will be conducted on the Safety Set. All safety data available at the time of database lock up to Day 183 will be provided in patient listings.

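### SAP 9.3: two Day 183 window ends in Table 4 follow neither stated end rule, and choosing the record nearest the window midpoint can displace the scheduled record, most clearly at Day 15

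*SAP*

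**What the plan says.** SAP Section 9.3 (Analysis Visits) defines "windows based on the list of visits described in the schedule of assessments of the protocol". In general each bound is the midpoint between adjacent target days, and a whole middle day opens the next window. The example runs "for an assessment with a scheduled visit on Day 127, and a prior scheduled visit on Day 99", with the next visit on Day 155, and gives Days 113–140. Windows are therefore built per assessment; Table 4 likewise leaves Days 43, 99 and 155 out of the FACIT-Fatigue/urinalysis block.

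The end rule is: "The upper bound of the last visit window is set as the target date + 7 days". The reader is then told: "Please refer to the following table for visit window definitions". Table 4 ends the Day 183 window at 196 (chemistry/hematology/vital signs), 210 (FACIT-Fatigue/urinalysis) and 266 (PNH clone).

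Out-of-window records are also assigned to a visit. With several records in one window, "the record closest to the midpoint of the interval will be used in the analysis"; ties go to the earlier record.

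On scope, SAP Section 4 says the plan "outlines only the analyses that are to be included in the report developed after the 26-week Primary Evaluation Period". In Section 7.2.2, LDH "will be summarized at all study visits up to Day 183 (Week 26) by both observed case (OC) and LOCF". Section 7.3 says: "All safety data available at the time of database lock up to Day 183 will be provided in patient listings". Protocol Table 1 (footnote a) places the Week 26 assessment before the Day 183 dose, and that dose starts the Extension Period.

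**The concern.** There are three linked problems.

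1. **End of the Day 183 window.** The text and Table 4 disagree whichever visit is taken as last. Programmers working from one or the other would build different Week 26 data sets.
2. **Selection.** Where a window is not centred on its nominal day, nearness to the midpoint favours an off-schedule record. Protocol Section 7.3 requires an LDH sample when breakthrough hemolysis is suspected, so a competing chemistry record is foreseeable. An event-triggered value would then stand in for the routine predose value in the by-visit LDH summary.
3. **Extension records.** Table 4 admits days well after Day 183, and the window rule does not exclude records taken after the first Extension dose. That limit is only implied elsewhere.

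The summaries exposed are LDH, free hemoglobin, FACIT-Fatigue, other laboratory values, vital signs, and clone size if it is summarized.

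**Working it through.** **Inputs.** Target days and printed bounds come from SAP Table 4. Later visits come from Protocol Table 2: chemistry, hematology, vital signs and urinalysis are next due on Day 239, and FACIT-Fatigue and PNH clone on Day 351. Day 211 is a q4w-only visit at which none of these is marked.

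**Formulas.** Lower bound = (previous + target)/2. Upper bound = (target + next)/2 − 1, because the middle day opens the next window. Last window: target + 7.

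**Reproducing the plan's figures.** Day 127 chemistry: (99+127)/2 = 113 and (127+155)/2 − 1 = 140, as in the SAP's example. Day 15 chemistry: (1+15)/2 = 8 and (15+43)/2 − 1 = 28. Day 15 FACIT-Fatigue ends at (15+71)/2 − 1 = 42. Day 71 clone: (1+71)/2 = 36 and (71+183)/2 − 1 = 126. Every bound after Day 1 reproduces, up to and including the start of the Day 183 windows. Only the Day 183 ends are in question.

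**Day 183 ends.**

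| Assessment | Target + 7 | Midpoint to its own next visit | Midpoint to Day 211 | Table 4 |
|---|---|---|---|---|
| Chemistry/hematology/vital signs | 190 | (183+239)/2 − 1 = 210 | (183+211)/2 − 1 = 196 | 196 |
| Urinalysis | 190 | 210 | 196 | 210 |
| FACIT-Fatigue | 190 | (183+351)/2 − 1 = 266 | 196 | 210 |
| PNH clone | 190 | 266 | 196 | 266 |

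The +7 rule matches no row. The assessment-level midpoint matches urinalysis and clone but not chemistry or FACIT-Fatigue. The Day 211 route gives 196 for chemistry, but would give 196 for FACIT-Fatigue too. No single reading yields both printed values.

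The printed ends lie 196 − 183 = 13, 210 − 183 = 27 and 266 − 183 = 83 days after Day 183.

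**Selection under Table 4 as printed.** For each window, a record on the nominal day was compared with one on every other day (nearest the midpoint wins, ties to the earlier).

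| Window | Days | Midpoint | Nominal-day record loses to |
|---|---|---|---|
| Day 15 chemistry | 8–28 | 18 | Days 16–20 |
| Day 15 FACIT-Fatigue/urinalysis | 8–42 | 25 | Days 16–34 |
| Day 71 clone | 36–126 | 81 | Days 72–90 |
| Day 183 clone | 127–266 | 196.5 | Days 184–209 |
| Other 9 windows | – | nominal − 0.5 | the day before only |

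The Day 15 result does not need a visit exactly on Day 15. Protocol Table 1's window is garbled in the text; reading it as ±3 days (an assumption), a chemistry visit on Day 12 loses to Days 13–23, Day 16 to Days 17–19, Day 17 to Day 18, and Day 18 to none. A FACIT-Fatigue visit on Day 12 loses to Days 13–37 and one on Day 18 to Days 19–31.

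**Day 183 if the ends are corrected but midpoint selection is kept.**

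| Assessment | End | Midpoint | Day 183 record loses to |
|---|---|---|---|
| Chemistry | 196 (printed) | 182.5 | Day 182 |
| Chemistry | 190 (+7) | 179.5 | Days 176–182 |
| Chemistry | 210 (midpoint rule) | 189.5 | Days 184–195 |
| FACIT-Fatigue | 210 (printed) | 182.5 | Day 182 |
| FACIT-Fatigue | 190 (+7) | 172.5 | Days 162–182 |
| FACIT-Fatigue | 266 (midpoint rule) | 210.5 | Days 184–237 |

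Each displacement needs an additional record on those days.

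**Weight of one patient.** 1/13 = 7.7% of a total-column mean, and more in the naïve and previously treated columns.

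**The case against.** The arithmetic is not in doubt; the case against is about importance.

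- The named LDH, FACIT-Fatigue and free hemoglobin endpoints are changes to Day 183, where the printed windows are centred within half a day. This stands: as printed, Week 26 is barely affected.
- Only Day 15 chemistry has a protocol-required trigger for a second record. A suspected breakthrough visit requires LDH, PK and PD, not a questionnaire, and clone size is named in the SAP only at screening. This also stands, so the FACIT-Fatigue and clone ranges show what the rule permits, not what is likely. A breakthrough event is not lost either: it has its own form, and all laboratory data are listed.
- The wider Day 183 ranges arise only if Table 4 is edited and midpoint selection kept. True, but the text and table must be reconciled, and moving the ends to either stated rule is an obvious way to do it.
- The SAP says its midpoint rule applies generally and sends the reader to Table 4, so Table 4 would probably be programmed. That predicts what happens, but leaves a contradicting sentence in the plan.
- A delayed Day 183 visit can still be predose, and other sections stop at Day 183. Correct; hence the limit should be tied to the dose, not the day number.
- The report in scope follows enrollment of 12 patients, not 13. Then 1/12 = 8.3%, which changes nothing of substance.
- Midpoint selection is prespecified and blind to outcome. It is, but where an event prompts the extra sample, the rule still favours that sample at Day 15.

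**Conclusion.** The concern holds and should be fixed, although its effect is small. Two Day 183 ends in Table 4, chemistry/hematology/vital signs (196) and FACIT-Fatigue (210), follow neither stated end rule, and the +7 sentence fits no block if Day 183 is the last visit. Under that reading, a chemistry record on Days 191–196 or a FACIT-Fatigue record on Days 191–210 is in by the table and out by the text.

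Midpoint selection works against the schedule in 4 of 13 post-baseline windows. The practical case is an LDH drawn for suspected breakthrough on Days 16–20 displacing a Day 15 value.

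Only by-visit descriptive summaries are touched, in patients with multiple, late or missing records. The PK/PD primary endpoint and the responder endpoints through Day 183 are not. The conclusion rests on building windows per assessment, as the SAP's example does. The figures for visits off Day 15 also rest on the ±3-day reading.

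**What to change.** In SAP Section 9.3:

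1. State which visit is last, give one end rule for Day 183, and make Table 4 follow it. If the midpoint rule is kept, split the FACIT-Fatigue/urinalysis row, since their next visits differ.
2. Restrict Day 183 (Week 26) records to those taken before the first Extension dose.
3. Select the record nearest the nominal day, ties to the earlier.

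Make these changes together. If Table 4 stays as printed, the third matters mainly for Day 15 and clone; if its ends move to either rule, it also matters for Day 183 chemistry and FACIT-Fatigue.

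Nominal-day selection fully protects a visit held on the nominal day, not one held off it. A Day 12 visit is 3 days from Day 15 and would still lose to Days 13–17, which are at most 2 days away. Giving scheduled records precedence over unscheduled ones would close that gap if the team wants it closed.

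The cost is some SAP wording, a few Table 4 cells and a small programming change before database lock. A few late records would leave the Week 26 observed-case summary.

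### SAP 9.3 selects the record nearest the window centre instead of the nominal day, so four off-centre windows in Table 4 can drop an on-schedule record; Table 4 also leaves some early days in no window (minor)

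*SAP*

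**What the plan says.** The rules are in SAP 9.3, under Analysis Visits, and in Table 4.

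- Coverage: "All post baseline records including those that occurred outside the specified protocol windows will be assigned to an appropriate analysis visit".
- Window bounds, set from neighbouring visits: "the lower bound and the upper bound for each analysis visit window is defined as the midpoint of the target dates between 2 consecutive scheduled". If the gap between two visits is an even number of days, "that middle day will be included in the lower bound of the next visit window".
- Last window: "The upper bound of the last visit window is set as the target date + 7 days".
- Several records in one window: "the record closest to the midpoint of the interval will be used in the analysis".
- Ties: "If 2 records are “tied” before and after the middle of the interval, the earlier record will be used in the analysis".

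Table 4 then gives start and end days for three groups of assessments. Day 1 is a one-day window in each. The next window starts on Day 8, or on Day 36 for PNH clone size. The clone rows after Day 1 read "Day 71 71 36 126" and "Day 183 183 127 266".

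SAP 7.2.2 uses these visits to summarise LDH, free hemoglobin and FACIT-Fatigue at each visit up to Day 183, by observed case and by LOCF. SAP 7.3.3.1 uses them for by-visit laboratory statistics and shift tables.

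**The concern.** A row labelled Day 15 should hold the record taken nearest Day 15. Selecting on the window centre does that only where the window is symmetric about the nominal day. Where the spacing before and after a visit differs, the centre moves towards the longer side, and a record taken exactly on schedule can lose to a later one.

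Second records are foreseeable. Protocol 7.3 allows unscheduled visits at the investigator's discretion and requires one, with a central-laboratory LDH sample, when breakthrough hemolysis is suspected between visits. The last column of protocol Table 1 doubles as the ET visit and repeats chemistry, hematology, urinalysis, FACIT-Fatigue and clone size. The replacement can also be informative. Scheduled Day 15 laboratory samples are predose; a Day 16-20 sample follows that dose if it was given on schedule, and may have been drawn because hemolysis was suspected.

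The second issue is coverage. A record on a day in no window cannot be assigned to a visit, whatever the text promises.

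**Working it through.** **Reproducing the SAP's own example.** For Day 127, with neighbouring visits on Days 99 and 155:
- start = (previous target + target)/2 = (99 + 127)/2 = 113
- end = (target + next target)/2 - 1 = (127 + 155)/2 - 1 = 140

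This matches the SAP's Days 113 to 140, so the bound rule is understood correctly.

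**Centre against nominal day.** Centre = (start + end)/2, with start and end from Table 4. A second record on day d replaces an on-schedule record if d is strictly nearer the centre, or equally near and earlier.

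| Window in Table 4 | Days | Centre | Centre minus nominal | Days that replace an on-schedule record |
|---|---|---|---|---|
| Chemistry/hematology/vital signs, Day 15 | 8-28 | (8+28)/2 = 18 | +3 | 16-20 (5 days) |
| FACIT-Fatigue/urinalysis, Day 15 | 8-42 | (8+42)/2 = 25 | +10 | 16-34 (19 days) |
| PNH clone, Day 71 | 36-126 | (36+126)/2 = 81 | +10 | 72-90 (19 days) |
| PNH clone, Day 183 | 127-266 | (127+266)/2 = 196.5 | +13.5 | 184-209 (26 days) |
| Every other window after Day 1 | | | -0.5 | only the day before the nominal day, by the tie rule |

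The last row includes Day 71 chemistry (57-84) and Day 71 FACIT-Fatigue (43-98), both centred on 70.5. It also includes Day 183 chemistry/hematology (169-196) and Day 183 FACIT-Fatigue (155-210), both centred on 182.5.

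**Example.** A child has a FACIT-Fatigue score on Day 15 and leaves on Day 30 with an ET score. Distances from centre 25 are |15 - 25| = 10 and |30 - 25| = 5. The ET score is reported as Day 15 and the true Day 15 score drops out of that row. The child's Day 30 chemistry falls in the Day 43 window (29-56) and replaces nothing at Day 15.

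**Uncovered days.** Between the end of the Day 1 window and the next start lie Days 2-7 (6 days) for the first two groups and Days 2-35 (34 days) for clone size. The bound rule in the text would have ended the Day 1 window on (1 + 15)/2 - 1 = Day 7, or (1 + 71)/2 - 1 = Day 35 for clone size. Table 4 departs from that rule without saying what happens to the days in between.

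**The case against.** The case for leaving the text alone has four parts.

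1. *The sponsor may have meant the nominal day.* Possibly, but a programmer following the words would code the window centre, so the words still need changing.

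2. *Displacement needs a second record in the same window.* This stands. After Day 15 the next scheduled chemistry visit is Day 43, so a competitor on Days 16-20 must come from an unscheduled visit or a very early termination. Clone size on Days 184-209 also needs a record after Day 183 to be in the data for the 26-week report.

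3. *The affected rows are not endpoint timepoints.* This stands. The LDH, free hemoglobin and FACIT-Fatigue endpoints run to Day 183. Clone size is neither a primary nor a secondary endpoint, and the only clone summary that the SAP names is at screening (7.1.3.2). Table 4 has no PK/PD rows, and SAP 7.2.1 uses actual sampling times. Transfusion avoidance and hemoglobin stabilization are judged over the whole period, and breakthrough hemolysis is captured as an event on its own form.

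4. *Nothing is scheduled on Days 2-7.* This stands as far as it goes. Only unscheduled records can fall there, and by-patient listings keep them. The clone gap is likewise free of scheduled clone samples. The contradiction with the coverage sentence remains.

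A reader might infer that Day 71 results in general are exposed, or that first-week safety data are lost. The documents support neither. The material Day 71 shift is for clone size alone, and early records are missing only from by-visit summaries.

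**Conclusion.** The selection rule is wrong as written and the coverage sentence contradicts Table 4, but the consequence is minor. It is confined to intermediate by-visit rows, chiefly Day 15, and to clone size, and it arises only when a second record exists. As a guide to size, with about 13 patients one substituted FACIT-Fatigue score that crosses the 3-point improvement threshold would move the total-group proportion at that visit by 1/13, or 7.7 percentage points. The step is larger within the naïve or eculizumab-treated group, or if some children are under 5 and not assessed. The study is descriptive, so no test result depends on it.

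It would be tempting to conclude that the Week 26 efficacy results or the primary PK/PD results are compromised. The documents do not support that: the Day 183 endpoint windows in Table 4 are half a day off centre, and no PK/PD window exists.

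This rests on two assumptions. First, the midpoint of the interval means the middle of the analysis window. Second, the end days printed in Table 4 govern. The text would end the last window on 183 + 7 = Day 190, whereas Table 4 prints Day 196, 210 or 266. Under Day 190 the Day 183 chemistry centre would be (169 + 190)/2 = 179.5 and the FACIT-Fatigue centre (155 + 190)/2 = 172.5, no longer within half a day of nominal. Text and table should therefore be reconciled in the same edit.

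**What to change.** In SAP 9.3:

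1. When a window holds several records, keep the one closest to the nominal day in Table 4, with ties to the earlier record. Prefer a scheduled-visit record over an unscheduled or ET record in the same window. No other day's record can then displace an on-schedule one.
2. State that LOCF still carries forward the last actual record, so an ET value not chosen for its window is not lost to the LOCF analysis.
3. For Days 2-7 (Days 2-35 for clone size), state that records are excluded from by-visit summaries but are listed and available for LOCF, and amend the sentence on assigning all post-baseline records to match. Do not stretch the first post-baseline window back to Day 2: that breaks the SAP's own midpoint rule and could report a Day 2 value as Day 15, or as Day 71 for clone size.
4. Reconcile the end of the last window between the text and Table 4.

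The cost is a few sentences and a small change to the visit-assignment program. No new data or visits are needed.

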7.3.2. Adverse Events (AEs)

Adverse Events (AEs) will be classified by System Organ Class (SOC) and Preferred Term (PT) using the latest available version of MedDRA and will be reported by naïve, previously eculizumab-treated patients and total. The adverse events will be determined as occurring prior to treatment (pre-treatment) or as on or after first treatment (treatment-emergent) as described in Section 9.3. Analyses of Pre-Treatment Adverse Events (PTAEs) and Treatment-Emergent Adverse Events (TEAEs) will be tabulated and presented separately. Patients having multiple AEs within a category (e.g., overall, SOC, PT) will be counted once in that category. For severity/relationship tables, the patient's highest grade/most related event within a category will be counted. Percentages will be based on the number of treated patients in the Safety Set within naïve, previously eculizumab-treated patients and total. Tables will be sorted by descending frequency of SOC and by descending frequency of PT within SOC.

Listings will be provided for all TEAEs and PTAEs for the Safety Set.

Adverse events will include the displays described in the following sub-sections.

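### SAP 9.3 read literally makes an AE dated on the first-dose day with no start time pre-treatment, although an AE with no start date at all is treatment-emergent

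*SAP*

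**What the plan says.** The operating rule is in the Adverse Events part of SAP 9.3. It has three steps.

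- **Definition.** Treatment-emergent AEs are "events with start dates and start times on or after the date and time of the first ALXN1210 dose". Date and time are both named.
- **Missing-data rules.** These open with the condition "If the start date of an AE is partially or completely missing", and apply provided the stop date and time do not place the event before first dose. If the start year is the first-dose year, the AE is treatment-emergent when the month is missing, or when "the start month is present and is the same or after the month of the first study drug dose". For an event with no start date the rule is: "If the start date is completely missing, then the AE is treatment-emergent".
- **Catch-all.** "All other AEs are considered Pre-Treatment Adverse Events (PTAEs".

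SAP 7.3.2 describes the post-dose group "as on or after first treatment (treatment-emergent" but refers to 9.3 for how the split is made. It also says that the two groups are tabulated separately and that both are listed for the Safety Set. Protocol 14.9.1 counts an AE as treatment-emergent if it begins during the first infusion or later, and has no rule for a missing time. SAP 4.1 declares no departure from the protocol's analyses.

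**The concern.** The definition needs a clock time to settle events on the day of first dose. The missing-data rules do not mention a missing time. An event with a complete first-dose date and a blank time therefore falls between the two and lands in the pre-treatment group. No rule sends it there deliberately; the catch-all does so by default.

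That outcome runs against the rest of the section, which resolves doubt towards treatment-emergent. It also affects the day of first exposure. Protocol 9.5 notes that reactions to monoclonal antibodies tend to begin during the infusion or soon after it, and Protocol 14.9.1 plans a summary of treatment-emergent events occurring during administration. An event filed as pre-treatment would be missing from that summary and from the overall treatment-emergent table in SAP 7.3.2.1.

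**Working it through.** The plan gives no figure to reproduce here. The check applies the SAP 9.3 rule literally to test events, then works out what one reclassified patient does to a percentage.

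**Step 1: classification.** Take an illustrative first dose at 10:00 on Day 1, with no stop date and time that places the event before it.

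| AE start as recorded | Step that decides | Result |
|---|---|---|
| Day 1, 10:30 | Definition met | Treatment-emergent |
| Day 1, 09:30 | Definition not met, so catch-all | Pre-treatment |
| Day 1, no time | Definition cannot be shown to be met; date is complete, so missing-data rules do not open; catch-all | Pre-treatment |
| Day 2, no time | Every time on that date is after the dose | Treatment-emergent |
| Month and year of first dose only | Same-month rule | Treatment-emergent |
| Year of first dose only | Missing-month rule | Treatment-emergent |
| Nothing recorded | Missing-date rule | Treatment-emergent |

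The third and fifth rows show the inconsistency. The untimed Day 1 event has everything the month-and-year event has, plus the day. Deleting the day from its record would change it from pre-treatment to treatment-emergent.

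**Step 2: comparison with the protocol.** Suppose the untimed Day 1 event did begin during the infusion. Under Protocol 14.9.1 it is treatment-emergent; under the literal SAP rule it is pre-treatment. If its order relative to the dose is unknown, the protocol does not settle it either. The two documents can therefore conflict, but need not in every case.

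**Step 3: effect of one patient.** SAP 7.3.2 counts a patient once per category and uses treated patients as the denominator. A percentage therefore moves only if the patient has no other treatment-emergent event in that category. When that holds, the shift is 100/n points:

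- n = 12, the enrollment trigger for the report this SAP covers (SAP section 4): 100/12 = 8.3 points.
- n = 13, the planned enrollment (Protocol 14.2): 100/13 = 7.7 points.

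Tables are also split by prior treatment. The documents do not give the group sizes, so no single figure can be stated. If both groups are non-empty, the smaller has at most 6 of 12 or 13 patients, and the shift there is at least 100/6 = 16.7 points.

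**Step 4: effect of the fix.** Making an untimed first-dose-day event treatment-emergent by default changes the third row only. The other six results stay the same.

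**The case against.** The strongest answer is that the trigger may never occur. The SAP definition refers to start times and stop times, so it presumes that they are collected. The eCRF is not among the documents, and nothing says that an AE time may be left blank. This stands: the frequency is unknown and could be zero.

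A reader might infer that first-infusion reactions will be dropped from the safety tables. The documents do not support that. Appendix B of the protocol has patients closely observed during each infusion and requires such events to be captured in source and on the eCRF. Protocol 9.2 has actual dose times recorded. A recognised infusion reaction is the Day 1 event least likely to lack timing, and Protocol 14.9.1 makes it treatment-emergent in any case. A vague symptom whose order relative to the dose was not noted is the more plausible candidate.

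Nor would the event be lost. It would appear in the pre-treatment tables and in the listings, where a reader of a descriptive study of about 13 patients could find it. No test or decision rule depends on the count.

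A programmer might also treat a missing time as a partly missing date, and the same-month rule would then give treatment-emergent. That reading is sensible, but the SAP does not state it: the condition names the start date only, and the catch-all is explicit. SAP 7.3.2 offers no way out because it points back to 9.3. The objection limits how likely and how large the problem is, but leaves the wording gap in place.

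**Conclusion.** The gap is real and minor. On its literal wording, SAP 9.3 files an untimed AE on the first-dose day as pre-treatment, while events with less date information default to treatment-emergent. This is inconsistent within the SAP and can contradict Protocol 14.9.1.

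The size is conditional. It requires that an AE start time can be blank, that the event falls on the first-dose date, and that the patient has no other qualifying event in the category. Where all three hold, one patient moves the total-column percentage by 8.3 points (12 patients) or 7.7 points (13), and by more within a prior-treatment group.

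Two stronger readings should be set aside. It does not follow that every misfiled patient lowers overall treatment-emergent incidence, because patients are counted once per category and many may have another event by Day 183. It also does not follow that all untimed AEs become pre-treatment: for a complete date after the first-dose date, the date alone is enough.

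**What to change.** Add one sentence to the Adverse Events part of SAP 9.3: if the AE start date equals the date of first dose and the start time is missing, the AE is treatment-emergent unless its stop date and time show that it occurred before the first infusion.

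This reuses the exception that the section already applies to missing dates, and removes the possible conflict with Protocol 14.9.1. The cost is the sentence and the matching line of programming. The downside is that an occasional Day 1 event that began before the dose will be counted as treatment-emergent, a direction of error the section already accepts for missing dates. If the eCRF already requires an AE start time, the sentence will have no effect on the results.
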